11.5 Treatment and Follow-up of Adverse Events

Adverse events, especially those for which the relationship to the study drug is possible, probable or remote, should be followed up until they have returned to baseline status or stabilised. If at follow-up, return to baseline status or stabilisation cannot be established an explanation should be recorded on the CRF.

Any newly emergent SAEs after treatment is discontinued or the subject has completed the study and is considered to be related to the IMP or study participation should be recorded and reported immediately. The post-study period for the purpose of SAE reporting is routinely for up to 30 days following last visit of the study or until SAE is resolved or stabilized. In certain cases, such as where the drug has a long half-life, a longer follow-up period may be required.

11.6 Pregnancy reports

A female clinical trial subject must be instructed to inform the Investigator immediately if she becomes pregnant during the study. Pregnancies occurring up to 90 days after the completion of the study drug must also be reported to the Investigator.

The Investigator should report all pregnancies in female clinical trial subjects to

within one working day of becoming aware of them using a clinical trial pregnancy reporting form.

All pregnancy reports will be captured in the safety database. This includes normal pregnancies without an AE.

Any subject who becomes pregnant during the study period must not receive additional doses of investigational product and will be withdrawn from the study. If the subject requests to know which treatment she received, this information will be provided to her.

The pregnancy should be followed for outcome of the mother and the child, including any premature terminations, and should be reported to any outcome.

for

12 STATISTICAL METHODOLOGY

A detailed Statistical Analysis Plan (SAP) which describes in more details the planned analysis and reporting for this study was signed on 26Jan2017. When differences exist in descriptions, explanations or definitions provided in the Study Protocol and the SAP, the SAP prevails.

12.1 Original Protocol Sample Size and Power Consideration

The planned sample size is 215 subjects, 86 in each of the two active groups and 43 in the placebo group.

The total sample size is therefore 240 (96 in each of the two active groups and 48 in the placebo group).

12.2 Randomization

The ratio of 1:2:2 between the placebo and the two active groups has been chosen in order to minimize the numbers of subjects undergoing two liver biopsies, while taking a placebo.

The randomization list was generated prior to the study initiation, using a computer-generated randomization list produced by a Sintesi statistician on behalf of the Sponsor. The randomization was performed in blocks, 48 blocks containing 5 subjects each in a 2:2:1 ratio (2 subjects for each of the active groups and 1 placebo).

The Interactive Web Response System (IWRS) procedure was used to allocate the subject to the treatment group. On the day of randomization, each subject was assigned a randomization number according to the randomization list. This number, allocated via the IWRS in sequential chronological order will replace the screening number. In addition to the subject number, the IWRS assigned a kit number. The subject was to be supplied and treated throughout the study with IMP/study drug labeled with the kit number assigned at each visit.

Please note that randomization was stratified by countries.

12.3 Data Analyses Sets

The following data analysis sets are defined for this study:

• Intention-to-Treat Analysis Set (ITT): In accordance with the intention-to-treat principle, all randomized participants will be included in this analysis set, according to the treatment group to which they were originally assigned to.

- Safety Analysis Set (ST): The Safety Analysis Set will include all randomized participants who took at least one dose of the study drug according to the treatment actually received. The ST analysis set will serve as the principal analysis set for safety assessments.
- **Full Analysis Set (FAS)**: The Full Analysis Set (FAS) will include all patients of the ITT population who have baseline and at least 1 post baseline efficacy assessment. The FAS analysis set will include efficacy observations that were collected up to, including Visit 10 (Week 52) and all NMRS measurements. Note that efficacy analyses for the liver biopsy derived parameters will use only the FAS described below.
- Full Analysis Set for Liver Biopsy Data (FAS_{biopsy}): The Full Analysis Set for Liver Biopsy Data (FAS_{biopsy}) will include all patients of the ITT population who underwent the baseline and the post baseline biopsies. This analysis set is defined as the vast majority of Israeli participants are lacking the pair of biopsies due to regulatory limitation.
- **Completers Analysis Set (CO)**: The Completers analysis set (CO) will consist of all randomized subjects who normally completed Visit 10 (end of treatment) according to the treatment actually received and underwent both pre-treatment and post-treatment NMRS assessments.
- **Per Protocol Analysis Set (PP)**: The Per-Protocol analysis set (PP) will consist of all randomized subjects who normally completed Visit 10 (end of treatment), underwent both pre-treatment and post-treatment NMRS assessments without any major protocol violations according to the treatment actually received.

12.4 Study Population Summary

The ITT analysis set will be used for the description of study population. Descriptive statistics of these data will be provided by treatment group and overall.

12.4.1 Subject Disposition

Data from subjects who are screened, randomized, subjects in the pre-defined analysis sets, subjects who complete the study, subjects underwent two MRI scans, subjects underwent two liver biopsies, and subjects who early terminated the study prior to week 52 and between weeks 52-65 will be summarized using descriptive statistics. Termination reasons will also be summarized by reason using descriptive statistics. The denominator for calculating percentages will be the set of the ITT.

12.4.2 Study Inclusion and Exclusion Criteria

The number and proportion (%) of the ITT analysis set subjects who failed to meet study inclusions/exclusion criteria will be reported.

12.4.3 Demographics and Baseline Characteristics

Baseline characteristics including demography, underlying disease characteristics, baseline physical examination and baseline efficacy endpoints will be provided in summary tables broken down by treatment groups and overall. Summary of these data will use the ITT Analysis Set.

For continuous variables, descriptive statistics (number [n], mean, standard deviation, standard error, median, minimum, and maximum) will be provided. For categorical variables, subject

counts and percentages will be provided. Categories for missing data will be presented if necessary.

12.4.4 Medical History

The incidence (no. of patients) will be provided when broken down by SOC and by SOC and Preferred Term according to MedDRA dictionary Version 19. Subjects with at least 1 abnormal finding and abnormal findings for each category will be summarized using descriptive statistics. Subjects will be counted only once in each category. Summary of these data will use the ITT Analysis Set.

12.4.5 Prior and Concomitant Medications

All prior and concomitant medications will be coded using the WHODRUG Sep 2016 DDE. The incidence of prior medications and separately those consumed concomitantly, from randomization day and onwards, to study will be summarized using descriptive statistics by therapeutic main group (ATC Level 2) and preferred term. Subjects will only be counted once in each Therapeutic Main Group, and only once in each Preferred Term category. Summary of these data will use the ITT Analysis Set.

12.4.6 Pre-Study Medications

Analyses will include only coded medications that were initiated prior to randomization date. Medications in which start date was not reported in database are also considered as pre-study medications. Incidence table including subject counts (no. of subjects) and percentages broken down by Therapeutic Main Group and Preferred Term as well as by treatment group will be generated.

12.4.7 Concomitant Medications

Analyses will include only coded medications that were consumed on randomization date or afterwards. Medications in which start date was not reported in database are also considered as concomitant medications. Incidence table including subject counts (no. of subjects) and percentages broken down by Therapeutic Main Group and Preferred Term as well as by treatment group will be generated.

12.4.8 Disallowed Medications Use

Disallowed medications will be listed. Summary table including subject counts (no. of subjects) and relative percentages when broken down by these two periods and overall will be displayed.

12.4.9 Physical Examination at Baseline

The number and proportion (%) of subjects' physical examination results at baseline will be tabulated.

12.4.10Protocol Violations/Deviations

Protocol deviations and violations are recorded in an Excel file maintained by the Sponsor.

Protocol No: 005 ARREST study

An incidence table displaying the number and proportion (%) of subjects with at least 1 protocol violation in each category will be summarized using descriptive statistics. Individual subjects listings will also be provided.

[figure not shown]
12.5 Significance Level and Multiplicity Adjustment

One (1) primary endpoint and 5 secondary end-points are pre-defined for each of the 2 Aramchol doses (400mg and 600mg) studied. The overall significance level for this study will be 5% using two-tailed tests utilizing the hierarchical gate keeping approach to control the overall Type-I error rate. Since two doses of Aramchol will be tested vs. placebo, there will be a total of 12 comparisons (contrasts) for the primary and secondary endpoints altogether.

According to the gate keeping approach, the 1st contrast (600mg vs. Placebo in the primary endpoint) will be tested using a two-tailed 5% significance level. If, the 1st contrast will statistically significantly favor the 600mg vs. Placebo in the primary endpoint, then the 2nd contrast (600mg vs. Placebo in the key secondary endpoint; Proportion (%) of Subjects with CRN Fibrosis Score Improvement) will be tested using a two-tailed 5% significance level. In the case the 1st contrast will fail to statistically significantly favor the 600mg vs. Placebo in the primary endpoint then significance testing will be ended failing to demonstrate statistically significant evidence in favor of both Aramchol doses (400mg and 600mg).

In the case that the 1st contrast will statistically significantly favor the 600mg vs. Placebo comparison, then the study will be considered successful as primary objective was met.

Nominal p values will be reported in the CSR in the case of failure to reach the above defined statistical significance.

12.6 Primary Efficacy Endpoint and Principal Statistical Analysis

The primary endpoint of the study is the percent (%) change from baseline to end of study in liver triglycerides ratio as measured by NMRS.

The Full Analysis Set (FAS) will be used as the primary analysis set for efficacy analysis and inference.

Data for this analysis will be retrieved from the central MRI reading center dataset specifically designed to capture multiple locations measurements of liver triglycerides ratios done for each MRI scan.

For each MRI scan, liver triglycerides ratios were reported as taken from one or several locations of the liver as deemed necessary by the MRI reading specialist. Furthermore, in some cases replications within liver location sites were also been performed to improve precision. These within location replications will be averaged, and the percent (%) change from baseline for matched locations will be calculated having in the analysis repeated measures (repeated per matched locations).

The statistical model will be a Mixed Model (SAS[®] MIXED procedure) with random intercept subcommand. The model will include the following covariates: treatment group, CGR1, age (1df), sex, baseline liver triglycerides ratio (1df) and baseline BMI (1df).

The model will be a Random Intercept model. The REML estimation method will be used and degrees of freedom will be adjusted using the Kenward-Roger method. The calculated percent change from baseline for each subject's liver location will be used as response in the model and differences between the treatments groups will be estimated using contrasts.

Protocol No: 005 ARREST study	CONFIDENTIAL Final	Version: May 03, 2017 Amended protocol #7

12.7 Key Secondary Endpoints and Analyses

Key secondary endpoints, with the exception of the liver biopsy derived endpoints, will be tested for the Full Analysis Set (FAS). Liver biopsy derived endpoints will be tested using the

Full Analysis Set for Liver Biopsy Data (FAS_{biopsy}). Controlling for multiplicity will be performed as detailed in Section 12.5.

As for liver biopsies derived endpoints, please note that biopsies were originally planned to be taken at screening and at study termination. However, pairs of biopsies will not be available for the vast majority of study participants from Israel as a second biopsy was not approved by regulatory authorities until September 2016. Also note that whenever CRN Fibrosis Score is mentioned in description of liver biopsies derived endpoints, the reference is made to database variable name "CRN Fibrosis Score (NAS)".

The key secondary endpoints for this study are provided below in the hierarchy order of analysis in employing the gate keeping approach:

12.7.1 Proportion (%) of Subjects with CRN Fibrosis Score Improvement

This endpoint will be derived from the liver biopsies dataset and analysis will use the Full Analysis Set for Liver Biopsy Data (FAS_{biopsy}).

A subject will be defined as a treatment responder in the case that the CRN Fibrosis Score is decreased as compared to screening by 1 point (stage) or more and there is no worsening of NASH defined by an increase of Inflammation (NAS) and or Ballooning (NAS) grades.

Baseline adjusted logistic regression (SAS[®] LOGISTIC procedure) stratified by CGR₂ using the STRATA sub-command with the following effects: treatment group, baseline CRN Fibrosis Score (1df) and NAS Score (1df) will be used to test the between the active groups and placebo contrasts.

12.7.2 Proportion (%) of Subjects with NAS Score Improvement without Worsening of CRN Fibrosis Score

This endpoint will be derived from the liver biopsies dataset and analysis will use the Full Analysis Set for Liver Biopsy Data (FAS_{biopsy}).

A subject will be defined as a treatment responder in the case that the NAS Score improvement (reduction as compared to baseline) will be of 2 point or more contributed by more than one of the following: Steatosis (NAS), Inflammation (NAS), Ballooning (NAS), pending of no CRN Fibrosis Score worsening.

Baseline adjusted logistic regression (SAS[®] LOGISTIC procedure) stratified by CGR₂ using the STRATA sub-command with the following effects: treatment group baseline CRN Fibrosis Score (1df) and NAS Score (1df) will be used to test the between the active groups and placebo contrasts.

12.7.3 Proportion (%) of Subjects with SAF Activity Score Improvement without Worsening of CRN Fibrosis Score

This endpoint will be derived from the liver biopsies dataset and analysis will use the Full Analysis Set for Liver Biopsy Data (FAS_{biopsy}).

A subject will be defined as a treatment responder in the case that the SAF Activity Score improvement will be of 2 point or more pending of no CRN Fibrosis Score worsening.

Baseline adjusted logistic regression (SAS[®] LOGISTIC procedure) stratified by CGR₂ using the STRATA sub-command with the following effects: treatment group, baseline CRN Fibrosis Score (1df) and NAS Score (1df) will be used to test the between the active groups and placebo contrasts.

12.7.4 Proportion (%) of Subjects with NASH Resolution without Worsening of CRN Fibrosis Score

This endpoint will be derived from the liver biopsies dataset and analysis will use the Full Analysis Set for Liver Biopsy Data (FAS_{biopsy}).

A subject will be defined as a treatment responder in the case that all of the below criteria are met:

- No worsening in CRN Fibrosis Score.
- NAS Ballooning Score equals 0 at termination.
- NAS Inflammation Score equals 0 or 1 at termination.

Baseline adjusted logistic regression (SAS® LOGISTIC procedure) stratified by CGR₂ using the STRATA sub-command with the following effects: treatment group, baseline CRN Fibrosis Score (1df) and NAS Score (1df) will be used to test the between the active groups and placebo contrasts.

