6.1 Inclusion Criteria

- 1. Male or female aged 18-75 years.
- 2. BMI between 25 Kg/m2 to 40Kg/m2, or waist circumference between 88cm to 200cm for women, and between 102cm to 200cm for men. If there is deviation above the upper limit, please consult the MRI center, to ensure that the machine is suitable for the patient.
- 3. Known type II Diabetes Mellitus or pre-diabetes according to American Diabetic Association. One of the following 3 criteria is needed for pre-Diabetic: Fasting Plasma Glucose > 100mg/dl (5.5 mmol/l) or 2hPG following 75g OGTT >140 mg/dl (7.8 mmol/l) or HbA1c > 5.7%. HbA1c can be repeated at Investigator's discretion.
- 4. Histologically proven Steatohepatitis on a diagnostic liver biopsy performed either during screening or within 6 months before screening visit, confirmed by central laboratory reading of the slides (steatosis ≥1 + inflammation ≥1 + ballooning ≥1). total activity NAS score of 4 or more

- 5. Liver fat concentration of 5.5% or more as measured by NMRS.
- 6. Biopsies with an activity NAS score of 4 or more.
- Normal synthetic liver function (serum albumin >3.2g/dl, INR 0.8-1.2, conjugated bilirubin < 35 μmol/L).
- 8. Understanding the nature of the study and signature of the written informed consent.
- 9. Negative pregnancy test at study entry for females of child bearing potential.
- 10. Females of child bearing potential practicing reliable contraception throughout the study period (including oral contraceptive). If barrier methods are used, it is recommended to practice two methods (e.g. male condom + female diaphragm with spermicide). For country-specific requirements (e.g. Germany) contraception failure rates (Pearl Index) should be under 1% in accordance with the recommendations of the CTFG Working Group on Contraception.
- 11. Hypertensive patients must be controlled by stable dose of anti-hypertensive medication for at least 2 months prior to screening.
- 12. Patients previously treated with vitamin E (>400IU/day), Polyunsaturated fatty acid (>2g/day), Ursodeoxycholic acid or fish oil can be included if drugs are stopped at least 3 months prior to diagnostic liver biopsy (and are not started during the trial). These treatments-dosages are allowed if they were stable for at least 12 months prior to biopsy and can remain stable throughout the study. (Dosages less than the amounts stated above are allowed without washout- or stable-period restrictions.)

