12.7.5 Change from Baseline to Week 52/Termination in ALT (U/L)

This endpoint will be derived from the central laboratory dataset. Analysis will include data obtained until Week 52/Termination. The Full Analysis Set (FAS) will be used for the analysis of this endpoint.

The statistical model will be a Mixed Model for Repeated Measures (MMRM) (SAS[®] MIXED procedure with REPEATED sub-command). The model will include the following fixed effects: categorical week in trial by treatment interaction, CGR₁ and baseline ALT value (1df). The model will use the unstructured covariance structure and the REML estimation method and degrees of freedom will be adjusted using the Kenward-Roger method. Data from all changes form baseline to scheduled post-baseline visits will be used as response in the model and differences between the treatments groups at Week 52/Termination will be estimated using contrasts.

Protocol No: 005 ARREST study

In case that the model will not converge, the Maximum-Likelihood (ML) estimation method will be used instead of the default Restricted ML (REML). If the model still does not converge, then a simpler covariance structure with less parameters will be used, according to the following order: Heterogeneous Autoregressive(1) [ARH(1)], Heterogeneous Compound Symmetry (CSH), Autoregressive(1) [AR(1)], and Compound Symmetry (CS).

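### The SAF-activity responder model in 12.7.3 leaves out baseline SAF activity; adding it costs almost nothing and brings a small gain in power

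*Combined protocol and SAP*

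**What the plan says.** Section 12.7.3 defines response as follows: "A subject will be defined as a treatment responder in the case that the SAF Activity Score improvement will be of 2 point or more", provided the CRN fibrosis score does not worsen. The analysis is a logistic regression on FAS_biopsy with CGR2 in the STRATA statement, and its effects are "treatment group, baseline CRN Fibrosis Score (1df) and NAS Score (1df) will be used to test the between the active groups and placebo contrasts". Nearly the same covariate sentence serves all four biopsy endpoints, 12.7.1 to 12.7.4.

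NAS is a different score from SAF activity. Section 12.7.2 builds NAS from three components: "Steatosis (NAS), Inflammation (NAS), Ballooning (NAS), pending of no CRN Fibrosis Score worsening".

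Elsewhere the plan adjusts each improvement or change endpoint for its own starting value:
- the primary model in 12.6 ("baseline liver triglycerides ratio (1df) and baseline BMI (1df");
- the fibrosis model in 12.7.1, through baseline fibrosis;
- the NAS model in 12.7.2, through NAS;
- the ALT model in 12.7.5 ("and baseline ALT value (1df").

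The key secondary endpoints are "provided below in the hierarchy order of analysis in employing the gate keeping approach". SAF activity is third of the five.

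**The concern.** Among the endpoints defined by change from baseline, SAF activity is the only one whose model lacks its own baseline. The covariate sentence looks carried over from the neighbouring endpoints, and no reason for the omission is given.

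Only power is at stake. Randomisation keeps the treatment comparison valid without the covariate. NAS recovers part of the information because it shares inflammation and ballooning with SAF activity, but it also carries steatosis. Power matters here because placebo is the smallest arm and FAS_biopsy loses most Israeli participants, for whom a second biopsy was long not approved (12.7).

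**Working it through.** **1. The plan's own figures.** Section 12.1 gives 86 + 86 + 43 = 215 evaluable and 96 + 96 + 48 = 240 in total, an implied loss of 1 − 215/240 = 10.4%. The sums agree. The visible text gives no response rate, effect or power for the SAF endpoint, so there is no power figure to reproduce and the inputs below are assumptions.

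**2. Assumptions.**
- The documents do not define SAF activity. It is taken as inflammation (capped at 2) plus ballooning.
- Entry requires "steatosis ≥1 + inflammation ≥1 + ballooning ≥1" and NAS of at least 4, so baseline SAF activity runs from 2 to 4. A 2-point fall is possible for everyone, and no patient is a non-responder by construction.
- Baseline grades: inflammation 1/2/3 at 0.45/0.45/0.10; ballooning 1/2 at 0.55/0.45 (0.50/0.50 in columns D and E below); steatosis 1/2/3 at 0.3/0.4/0.3.
- The resulting correlation of SAF activity with NAS is 0.60. Since 0.60² = 0.36, NAS explains about a third of the variation in SAF activity.
- Placebo response is about 20%. CGR2 is not defined in the visible text, so four groups are assumed. The 600 mg vs placebo contrast is tested at two-sided 5%.

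**3. How prognostic might baseline SAF be?** Call the log-odds of response per SAF point γ.
- If inflammation and ballooning shift independently and only the floor of each scale matters, response at SAF 2/3/4 is 12/15/19%, 16/21/28% or 25/31/40% under three sets of shift probabilities. Then γ ≈ [logit(SAF 4) − logit(SAF 2)]/2. These rounded rates give (−1.45 + 1.99)/2 = 0.27, (−0.94 + 1.66)/2 = 0.36 and (−0.41 + 1.10)/2 = 0.35, so roughly 0.25 to 0.36.
- If each point is lost with the same patient-level chance, placebo response is 7/15/22% or 12/24/33%. That gives γ of (−1.27 + 2.59)/2 = 0.66 and (−0.71 + 1.99)/2 = 0.64.
- γ = 1.5 over a 2-point range is an odds ratio of e^3.0 ≈ 20, which is a stress test.

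**4. Power, model as written → with baseline SAF added.** Columns A and B use the conditional likelihood, as STRATA does (4000 trials each), with 75/75/38 pairs at odds ratios 3.0 and 2.46. Columns C to E use stratum indicators at odds ratio 3.0 with 75/75/38, 86/86/43 and 70/70/35 pairs (3000 trials each in D and E).

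| γ | A | B | C | D | E |
|---|---|---|---|---|---|
| 0 | 0.670→0.671 | – | 0.667→0.666 | 0.740→0.742 | 0.623→0.625 |
| 0.3 | – | – | 0.662→0.666 | – | – |
| 0.5 | 0.652→0.655 | 0.452→0.461 | 0.653→0.660 | 0.727→0.728 | 0.636→0.637 |
| 1.0 | 0.585→0.617 | 0.414→0.433 | 0.610→0.630 | 0.679→0.705 | 0.590→0.613 |
| 1.5 | 0.527→0.567 | 0.371→0.408 | 0.536→0.592 | 0.607→0.660 | 0.504→0.551 |

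In A and B the paired Monte Carlo standard error of a difference is at most 0.6 points. Varying placebo response over 15–25% gives gains of up to 5.8 points. The equal-chance model of step 3 gives 0.621→0.623 and 0.668→0.671 at 86/86/43, and 0.515→0.517 and 0.554→0.569 at 70/70/35. The largest drop in any run was 0.4 points, in a run where baseline SAF had no effect.

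**5. Type I error.** Null rejection is 0.048 without and 0.045 with the covariate in the conditional analysis. With stratum indicators it is 3.6–5.2% without and 3.9–5.0% with it.

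**6. Add SAF, or swap it for NAS?**
- SAF prognostic at γ = 1.5, steatosis not: swapping 0.569, adding 0.567.
- SAF and steatosis both at slope 0.5: as written 0.645, swapping 0.631, adding 0.646.
- Both at slope 1.0: as written 0.573, swapping 0.535, adding 0.575.

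Swapping can lose power. Adding does not.

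**7. The testing sequence.** If SAF is reached with an assumed probability of 0.3 to 0.6, the largest gain of 5.8 points becomes 1.7 to 3.5 points. A 1-point gain becomes 0.3 to 0.6.

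**The case against.** The strongest reply is that this is a reviewer's preference about one covariate. At the slopes that component-level reasoning supports, the gain is about the size of the simulation error. Gains of 2 points or more need slopes of 1.0 to 1.5, which nothing in the documents supports. That is right, and it is why the point is rated on its negligible cost and not on a large benefit.

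It can also be said that 12.7.3 follows a pattern: the four biopsy endpoints share one histology set, and 12.7.4 also lacks component baselines. A common set is defensible. But NASH resolution is defined mainly by the state at termination, whereas SAF response is a change from a baseline score that must already be on file.

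Three cautions stand.
- Adding a prognostic covariate to a logistic model changes the conditional odds ratio. At γ = 1.0 in column D the mean log odds ratio goes from 1.13 to 1.19 and its standard error from 0.472 to 0.487. This is a reason to settle the model before unblinding, not a reason against the covariate.
- Placebo responders would be few: 38 × 0.20 ≈ 8. No power loss beyond simulation error appeared at that size, but only four strata were examined.
- The sequence must pass the primary 600 mg contrast (12.5) as well as fibrosis and NAS before SAF is tested.

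**Conclusion.** The concern holds as a matter of precision. Baseline SAF activity is absent from the 12.7.3 model although it defines the endpoint and is available for every FAS_biopsy patient. Adding it gains nothing if it is not prognostic and about 1 point of power at plausible slopes (at most 1.5 points in the component-level runs). The gain is 2 to 3 points at a slope of 1.0 and about 4 to 6 at a slope of 1.5.

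The omission is certain. The size of the benefit rests on the assumed SAF definition, grade distribution, response rates, number of pairs and CGR2 grouping. The change is worth making because its cost is close to nil, but it should not rank high among the changes to the plan.

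**What to change.** In 12.7.3, add baseline SAF activity score from the screening biopsy, as a linear term with 1 degree of freedom, to the listed effects. Keep baseline fibrosis and NAS, and do not swap SAF for NAS. Section 12.7.1 needs no change.

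Make the same edit in the SAP signed on 26 January 2017, since section 12 says that document prevails. Its separate text was not available here, so its covariate list should be checked first.

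The cost is one line of wording and one degree of freedom. FAS_biopsy requires both biopsies and the endpoint cannot be derived without the baseline score, so no new data are needed. The change should be final before unblinding.
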